**Second interim analysis re-assessment:**

Based on the results of the second interim analysis executive committee suggested to increase the sample size to **760 patients** to compensate the technical data loss.

**Third interim analysis re-assessment:**

It was planned that we would re-estimate the coefficient of variation (CV) at 50% of planned enrollment. From the current sample of patients, the CV was estimated as 1.30 (up from 1.00). Using the re-estimated CV and assuming a 10% drop-out rate, we would need 1060 patients total (530 in each group) in order to have 90% power to detect a geometric mean ratio of 0.80 at a significance level of 0.05.

[figure not shown]

Figure 1: Efficacy and futility boundaries (non-binding) for the study design

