#### **Primary Analysis**

The effect of pre-operative patient education on cumulative opioid consumption (morphine equivalents) during first 72 postoperative hours will be assessed by using a t-test on the log transformed opioid consumption. Linear regression will be used to adjust for imbalance if necessary. The 95% CI for the ratio of geometric means (intervention/placebo) between the two groups will be reported.

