### ***H. Sample Size Calculations***

The coefficient of variation (CV) for cumulative opioid consumption was estimated to be 1.32 using a previous study. However, for our sample size calculations, we assume a lower CV of 1.00 because--unlike the previous study--we will be excluding patients with a history of opioid use in the past 3 months.

Based on the primary outcome of cumulative opioid consumption during the first 72 post-operative hours and assuming a CV of 1.00 we would need a total of 588 patients to have 90% power to detect a 20% decrease in opioid consumption at the 0.05 significance level. Planning for 3 interim analyses and one final analysis, we would require a maximum of **672 patients**. The boundaries for the analysis [efficacy (futility)] are:  $P \leq 0.002$  ( $P > 0.926$ ),  $P \leq 0.005$  ( $P > 0.624$ ),  $P \leq 0.015$  ( $P > 0.2011$ ), and  $P \leq 0.044$  ( $P > 0.044$ ).

**Internal Pilot Study to Re-assess Variability in Primary Outcome.** The coefficient of variation will be re-assessed via an internal pilot study at 50% of the planned enrollment, and sample size will be increased if needed. For a CV of 1.32 and planning for three interim analyses and one final analysis, we would need a maximum of **974 patients**.

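### The final efficacy boundary belongs to the 672-patient design and was not adapted when the sample size rose to 760 and then 1060, so the 5% error rate of the primary test is not protected

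*Combined protocol and SAP*

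**What the plan says.** The Interim Analysis section sets three looks, at 25%, 50% and 75% of planned enrolment, with gamma spending (−4 for efficacy, −1 for futility) and non-binding boundaries. Section H, Sample Size Calculations, gives a maximum of 672 patients. It lists the efficacy limits once, for that design: P ≤ 0.002, 0.005, 0.015 and, at the end, 0.044. The futility limit at the third look is P > 0.2011.

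Section H also plans one internal pilot re-assessment of the coefficient of variation (CV), "at 50% of the planned enrollment, and sample size will be increased if needed". It gives 974 patients as the maximum for a CV of 1.32.

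Two increases followed.
- After the second look: "Based on the results of the second interim analysis executive committee suggested to increase the sample size to" 760, with technical data loss as the stated reason.
- After the third look, to 1060. The Third interim analysis re-assessment recalls the schedule ("It was planned that we would re-estimate the coefficient of variation (CV) at 50% of planned enrollment") and then reports: "From the current sample of patients, the CV was estimated as 1.30 (up from 1.00"). The target is "90% power to detect a geometric mean ratio of 0.80 at a significance level of 0.05", with 10% drop-out.

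The Primary Analysis section says that the primary outcome "will be assessed by using a t-test on the log transformed opioid consumption". It does not mention the boundary or the changes in size. Section G, Statistical Plan, sets P < 0.05 for all analyses.

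**The concern.** Both increases came after unmasked-type comparisons for efficacy and futility, and the CV-based one came a look later than scheduled. The plan masks caregivers and evaluators. It does not say whether the executive committee was masked to the treatment effect, or whether the CV was estimated from blinded data.

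Two things follow. First, a boundary derived for looks at 25%, 50%, 75% and 100% of 672 no longer spends exactly 5% when the last analysis moves out to about 1000 patients. This holds whatever the motive for the change. Second, a t-test that weights all patients equally is open to challenge if the decision to extend depended on the observed effect, and the documents cannot exclude that. A positive primary result could be disputed on either ground. The increases cannot be undone, but the final statistic and threshold can still be fixed until the final unblinding.

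**Working it through.** **Inputs.** Section H: geometric mean ratio (GMR) 0.80, 90% power, level 0.05, CV 1.00 at design, and the boundaries above. Third interim re-assessment: CV 1.30, 10% drop-out, total 1060. Section D: 1:1 allocation. The documents do not say that the test is two-sided; this is inferred because it reproduces their figures. Actual counts at the looks are not given. I assume 168, 336 and 504 (25%, 50% and 75% of 672) and a final analysis at 954 (1060 × 0.9) to 1060.

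**The plan's own figures.** Log-scale SD = √ln(1 + CV²), which is 0.8326 for CV 1.00 and 0.9948 for CV 1.30. δ = |ln 0.80| = 0.2231. Total N ≈ 4·SD²·(1.960 + 1.282)²/δ², refined with the noncentral t.
- CV 1.00: 588 (stated 588).
- Four-look design, inflation 1.1396: 588 × 1.1396 = 670 (stated 672).
- CV 1.32: 854 × 1.1396 = 973 (stated 974).
- CV 1.30: 838 × 1.1396 = 955, and 955/0.9 = 1061 (stated 1060). Without the sequential inflation, 838/0.9 = 931.

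The spending function α(t) = 0.05(1 − e^{4t})/(1 − e^{4}) gives cumulative 0.0016, 0.0060, 0.0178 and 0.05 at the four looks. The matching nominal P values are 0.0016, 0.0048, 0.0147 and 0.0440, in line with the stated boundaries.

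**Effect of moving the final analysis.** Under no effect, the statistics at looks with n₁ < n₂ patients have correlation √(n₁/n₂). For the third look and the final analysis this is √(504/672) = 0.87 as designed, √(504/954) = 0.73 at 954 and √(504/1060) = 0.69 at 1060. With lower correlation, fewer final rejections overlap with earlier ones, so the same 0.044 spends more. Recursive integration with the stated boundaries and futility ignored gives:

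| Final analysis | First three looks | Final look at 0.044 | Total at P ≤ 0.044 | Total at P < 0.05 |
|---|---|---|---|---|
| 672 | 1.8% | 3.2% | 5.0% | – |
| 954 | 1.8% | 3.6% | 5.4% | 5.9–6.0% |
| 1060 | 1.8% | 3.7% | 5.5% | 6.0–6.1% |

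The ranges in the last column reflect exact against rounded early boundaries. If the third look was at 570 (75% of 760), the figures move by about 0.1 point. The final threshold that restores 5.0% is about P ≤ 0.038–0.040.

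**Late CV re-estimation alone.** In a simulation of 2,000,000 trials with the final size set only by the CV at the third look, type I error at 0.044 was 5.0% for a true CV of 1.00 and 5.4% for 1.30, with blinded or unblinded variance. The 5.4% equals the figure from the shifted information fractions, so lateness alone adds almost nothing.

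**If extension had depended on the third-look effect** (672 or 954 at the end, threshold 0.044):
- extend whenever P > about 0.10: 6.0%;
- extend only for P between 0.10 and 0.2011: about 5.2%;
- futility obeyed at every look, least favourable choice of size: 4.6%.

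If the final size could be anything from 672 or 760 up to 1060, the upper bound is 6.0–6.2%.

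**Weighted test.** With planned weights and P ≤ 0.044, type I error is about 5.0% whatever the final size. At GMR 0.80 and CV 1.30, with 954 patients and futility ignored, power falls from 93.0% to 91.3%. With futility obeyed it is 83.5% for the ordinary test and 83.8% for the weighted one. These powers were computed with two-stage weights 0.75 and 0.25. They carry over to the three-stage form when looks fall at 336 and 504, because √0.75 × √(336/504) = √0.50.

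**The case against.** A reader might infer that the plan treats the sample size as fixed. It does not: it sets a group-sequential design with a final boundary of 0.044, and 1060 is reached only with that design's inflation.

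A reader might also infer that the trial was extended because of the observed effect. The documents do not support this. The stated reasons are data loss and the CV. Section H had said in advance that the size would rise if needed, and 954 evaluable patients lie within its 974. Only the timing departs from the plan, and the section heading and the Summary of Changes both show the third look openly.

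Nor should 6.0% be read as the likely error. It requires enlarging the trial after the third-look futility line was crossed. Futility is non-binding, so 6.0% is a legitimate upper bound, but no more than that.

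Finally, the 0.05 in the Third interim analysis re-assessment can be read as the overall level, which is compatible with 0.044 at the last look. That reading does not rescue Section G, which applies P < 0.05 to all analyses, or the Primary Analysis section, which cites no boundary.

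What stands is that the boundary was never adapted to the new size, masking of the decisions is undocumented, and two thresholds coexist for one test.

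**Conclusion.** The concern holds in a limited form. With the boundaries left as they are, type I error is 5.4–5.5% at P ≤ 0.044 and 5.9–6.1% at P < 0.05, even if both increases were fully masked. The excess is modest: about half a point at 0.044, and about one point if 0.05 is applied.

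Dependence on the observed effect is neither shown nor excluded. At 0.044 its bound is about 6.0% if extension past futility is allowed, about 5.2% if extension stays inside the third-look futility line, and 4.6% if futility was always obeyed.

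These figures assume a two-sided test, looks at 168, 336 and 504 patients, and a final analysis at 954 to 1060. Except for the 4.6%, they also assume that futility is not binding. They should be recomputed from the actual counts.

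**What to change.** Make these changes before the final unblinding.

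1. In Primary Analysis, define the confirmatory statistic as Z = √0.50·Z(patients up to look 2) + √0.25·Z(patients between looks 2 and 3) + √0.25·Z(patients after look 3), each from the log-scale comparison, judged against P ≤ 0.044. Report the ordinary t-test and geometric mean ratio alongside. Three stages are needed. A two-part statistic that pools everyone up to the third look does not cover a result-dependent increase at the second: if the third look moved from 504 to 570 whenever the second-look P exceeded 0.10, simulation gives 5.3%.
2. State who saw unblinded results and on what data the CV was estimated. If records show that both decisions were masked to the effect, it is sufficient instead to re-derive the final boundary from the spending function at the actual information fractions (about P ≤ 0.039 under these assumptions).
3. In Section G and the Third interim analysis re-assessment, replace 0.05 with the chosen boundary for the primary test. If 0.05 is kept anywhere as the overall level, say so.
4. In the January 2023 entry of the Summary of Changes and in the Third interim analysis re-assessment, say that the re-estimation was made at the third look and not at the planned 50%.

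The cost is SAP wording, one extra line of analysis and, for the weighted test, about 1.7 points of power at 954 patients. Patients after the third look count for somewhat less in that test. No extra patients are needed.
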